### 7.4.4 Concomitant Procedure, Elective Procedure or Hospitalization

Concomitant procedure, elective procedure or hospitalization will be listed without summary.

#### 7.5 Efficacy

The best overall response will be calculated following RECIST guideline (version 1.1) by using the best response from visits where tumor assessment is performed. For subjects who discontinue from study, experienced progressive disease, died, or had anticancer therapy, tumor-directed radiotherapy, tumor-directed surgery, the tumor assessment up to the earliest date of the above mentioned events will be included in the best overall response calculation. The best overall response will be calculated respectively for the response assessed by investigator and the central review. Complete or partial response requires confirmation at a subsequent time point at least 4 weeks after the initial response is observed. Establishment of stable disease requires a minimum 42 day duration from first dose of study drug.

For this study, the date of investigator assessed timepoint response will be derived as follows:

- If the timepoint response is CR, PR or SD, the latest scan date, either from target or nontarget lesion will be used as the timepoint response date.
- If the timepoint response is PD, the scan date of earliest sign of progression, either from target or non-target lesion, or new lesion, is used as the timepoint response date.

Efficacy summaries of objective response rate (ORR) and duration of response (DOR) will be provided for the response-evaluable population for investigator assessment as well as central review assessment. The summaries for OS and PFS will be performed for safety population. Response beyond disease progression will not be included in the analysis. If the sample size is too small to do a certain analysis in a group, number and percent of subjects will be provided. For PFS, DOR, and ORR, the main analysis is based on investigator's assessment; the secondary analysis is based on assessment made by central review committee. Additionally, summary of ORR will be performed for the safety population for investigator assessment.

The by prior line of therapies (<=1 and >=2) subgroup analysis will be performed for PFS and OS for pancreatic cancer subjects.

Time to event distribution (e.g. progression free survival, overall survival, and duration of response) will be estimated using Kaplan-Meier (K-M) method. When appropriate, the median along with 95% CI will be provided using Brookmeyer and Crowley methodology(using log-log transformation for constructing the confidence intervals). Rates at fixed timepoints will be derived from the K-M estimate and corresponding confidence interval will be derived based on Greenwood formula. Confidence intervals for binomial proportions will be derived using the Clopper-Pearson method.

## 7.5.1 Primary Efficacy

## Summary:

- ORR with corresponding 2-sided 95% CI based on Clopper-Pearson method along with each category of BOR for response-evaluable population based on investigator assessment. Time to response will be also included.
- ORR with corresponding 2-sided 95% CI based on Clopper-Pearson method along with each category of BOR for safety population based on investigator assessment.

ORR is defined as total number of subjects with confirmed responses of either CR or PR divided by the total number of subjects in the respective population per RECIST v1.1 by investigator assessment. Time to response will be also included.

#### 7.5.2 Secondary Efficacy

Summary:

OS by K-M method. The median survival time along with 95% CI as well as OS rate at 4 months, 6 months, and 12 months will be presented by K-M analysis. OS will also be summarized descriptively (mean, standard deviation, median, first and third quartiles, minimum, maximum). The summary is for safety population.

OS is defined as the time (months) between the first dose of study drug and death due to any cause. Subjects will be censored for this endpoint on the date of the last known date alive if they do not die. The subgroup OS summary will be performed for subjects with pancreatic cancer by prior line of therapies ( $\leq 1$  and  $\geq 2$ ).

- PFS by K-M method for safety population based on investigator assessment
- PFS by K-M method for safety population based on central review assessment
- Subgroup PFS analysis by prior line of therapies (<=1 and >=2) for subjects with pancreatic cancer safety population based on central review assessment.

Sensitivity analysis will be performed for the above PFS analyses by treating clinical PD as event as well. Last dose date + 14 days is considered as event date for clinical PD.

PFS will be defined for each subject as the time (months) from the first dose to the first objectively documented disease progression per RECIST v1.1 or death due to any cause in the absence of documented PD. Censoring for the PFS endpoint is summarized in Table 3. PFS rate at specified timepoints (4 months, 6 months, 12 months) will be presented using K-M method.

- Duration of response (DOR) for responders (confirmed CR or PR) for response-evaluable population based on investigator assessment
- Duration of response (DOR) for responders (confirmed CR or PR) for response-evaluable population based on central review assessment

DOR is defined as the time (months) from date of the first documentation of confirmed response (CR or PR) to the first objectively documentation of progressive disease (PD) or to death due to

any cause in the absence of documented PD. The censoring mechanisms for DOR are similar to those for PFS.

- ORR with corresponding 2-sided 95% CI based on Clopper-Pearson method along with each category of BOR for response-evaluable population based on central review assessment. Time to response will also be included.
- ORR with corresponding 2-sided 95% CI based on Clopper-Pearson method along with each category of BOR for safety population based on central review assessment. Time to response will also be included.
- The extent of follow-up defined as the time between first dose date and last known date alive (for subjects who are alive) or death date (for subjects who died) will be summarized descriptively for safety population.

Situation	Date of Progression or Censoring	Outcome
No baseline or no evaluable baseline assessment, and no death	Date of first dose	Censored
No post baseline or no evaluable post baseline assessment, and no death	Date of first dose	Censored
No death or disease progression	Date of last evaluable assessment	Censored
Discontinued from study	Date of last evaluable assessment	Censored
New anticancer therapy, tumor- directed radiotherapy, or tumor- directed surgery received without progression reported prior or on the same day	Date of last evaluable tumor assessment prior to the date of initiation of subsequent anticancer therapy	Censored
Disease progression or death	Date of death or first documented progression per RECIST 1.1, whichever is earlier (excludes clinical progression)	Progressed (event)

Table 3: Handling of Missing Assessments and Censoring Rules for PFS

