### 7.4.2 Efficacy Analyses

For each disease type, response to treatment will be summarized for ORR, defined as the ratio of the number of patients that achieve an objective response (a BOR of CR or PR) to total number of patients who are evaluable for a response. Exact confidence interval will be constructed for the response rate. Overall Survival, survival at 1 year, and median survival will be estimated by the Kaplan-Meier method. The corresponding confidence interval will also be presented.

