### 7 STATISTICAL ANALYSES

### 7.1 General Methods

The statistical analysis will be conducted following the principles specified in the International Conference on Harmonisation (ICH) Topic E9 Statistical Principles for Clinical Trials (CPMP/ICH/363/96).

All statistical tabulations and analyses will be done using SAS®, Version 9.3 or higher.

Unless otherwise noted, continuous variables will be summarized using number of non-missing observations (n), arithmetic mean (mean), standard deviation (SD), median, minimum, and maximum; categorical variables will be summarized using the frequency count and the percentage of subjects in each category.

In the data listings, study day relative to first dose of study drug may be presented. Study day relative to first dose will be calculated as: event date – first dose date in the study (+ 1 if event date  $\geq$  first dose date in the study).

When appropriate, baseline is defined as the last non-missing result with a collection date-time less than the date-time of the first dose of study medication. If time is missing, unless otherwise specified, baseline is the last non-missing result prior to or equal to the date of first dose of study drug.

Unless otherwise specified, non-efficacy analyses except for biomarker and PK parameters, will be presented by:

- Overall monotherapy cohorts; overall combination cohorts
- individual or combined cohort by different dose and regimen

For efficacy and biomarker analyses, unless otherwise specified, the summary will be presented by:

- Pancreatic cancer cohort subjects dosed with 4 mg/kg cabiralizumab + 3 mg/kg nivolumab every 2 weeks, i.e., cohort 1aE4+1b4
- Pancreatic 6mg/kg cohort, i.e., cohort 1aC4
- Other individual cohort

PK analyses will be presented by individual or combined cohort by different dose and regimen.

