## Figure:

- Percent change from baseline in target lesions over time (spider plot)
- Best Change from baseline in target lesions (waterfall plot)

- K-M plot of DOR for responders based on investigator assessment only when number of responder is not few
- K-M plot of DOR for responders based on central review assessment only when number of responder is not few
- K-M plot of PFS for safety population. Two sets of figures, one based on investigator assessment and the other based on central review assessment, will be provided.
- Subgroup K-M plot of PFS analysis by prior line of therapies (<=1 and >=2) for subjects with pancreatic cancer safety population based on central review assessment
- K-M plot of OS for safety population
- Subgroup K-M plot of OS analysis by prior line of therapies (<=1 and >=2) for subjects with pancreatic cancer safety population

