## Listing:

The following will be listed for all subjects:

- Tumor lesion measurements
- Tumor evaluation at each visit
- Subject level efficacy for all treated subjects tumor best overall response (BOR), maximum response in tumor burden, PFS, death indicator
- Duration of response for responders BOR, time to response, time on therapy, response duration, response duration after treatment discontinuation, reason for treatment discontinuation
- Survival survival status, first dose date, last dose date, first subsequent anti-cancer therapy date, last known alive date, death date, time to death

For the above listings except for survival, assessment performed by investigator and central review committee will be listed separately.

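### The plain mean, SD, median and quartiles that SAP 7.5.2 plans for OS are follow-up statistics under an OS label, and the mean is too low whenever anyone is censored

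*SAP*

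**What the plan says.** SAP 7.5 sets one method for all time-to-event endpoints: "Time to event distribution (e.g. progression free survival, overall survival, and duration of response) will be estimated using Kaplan-Meier (K-M) method". Protocol 7.4.2 does the same for survival: "Overall Survival, survival at 1 year, and median survival will be estimated by the Kaplan-Meier method". It asks for no other OS summary.

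SAP 7.5.2 follows this with a Kaplan-Meier median, its 95% CI, and OS rates at 4, 6 and 12 months. It then adds that "OS will also be summarized descriptively (mean, standard deviation, median, first and third quartiles, minimum, maximum"), and names the safety population. Its censoring rule is: "Subjects will be censored for this endpoint on the date of the last known date alive if they do not die". Nothing says how a censored time enters a mean, an SD or a quartile. The section asks for no such summary of PFS or DOR.

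Later in the same section a separate item is planned: "The extent of follow-up defined as the time between first dose date and last known date alive (for subjects who are alive") or to the death date for those who died. It too is summarised descriptively in the safety population. Under SAP 7.1, by default, "continuous variables will be summarized using number of non-missing observations (n), arithmetic mean (mean), standard deviation (SD), median, minimum, and maximum".

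**The concern.** The same per-subject number appears to be tabulated twice, once under its proper name and once as survival. A follow-up time cut off by censoring is not a survival time. Its mean and upper quartile depend on how long subjects have been followed as well as on how long they live.

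Three things are at stake:

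- **Two medians for one endpoint.** The protocol names median OS as a Phase 1b secondary endpoint (synopsis and 7.3.2.2). A second, always finite, median could stand beside the Kaplan-Meier one, even where the latter is not reached.
- **A mean OS that is too low.** The reader is not told that it is a mean of follow-up.
- **Spurious differences.** Cohorts with identical survival but different follow-up would show different mean OS.

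**Working it through.** The documents state no OS mean, median or event count, so there is no planned figure to reproduce. The check uses the definitions, then algebra, then assumed scenarios.

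**1. Same variable.** Let T be time from first dose to death, and C time from first dose to the date last known alive for a subject who has not died.

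| | Died | Alive |
|---|---|---|
| OS analysis time (SAP 7.5.2) | death date − first dose | last known alive − first dose |
| Extent of follow-up (SAP 7.5.2) | death date − first dose | last known alive − first dose |

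Both equal X = min(T, C) for every subject, in the same population. Given the SAP 7.1 default statistics, the OS line adds only the two quartiles.

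**2. Direction of the error.** X ≤ T for everyone and X < T for each censored subject. So mean(X) < mean(T) once one subject is censored, whatever the distribution.

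Example: true times 2, 4, 6, 10 and 20 months, all followed to month 9.

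- True mean: 42/5 = 8.4.
- Plain mean: (2 + 4 + 6 + 9 + 9)/5 = 6.0.
- Deaths only: (2 + 4 + 6)/3 = 4.0.

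**3. Size.** Assumptions: exponential T with λ = ln 2/median, and independent C uniform on (a, b) months. Then

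- P(censored) = [exp(−λa) − exp(−λb)] / [λ(b − a)]
- E[X] = (1 − P(censored))/λ, so the relative shortfall of the mean equals the censored share.

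Median 12, follow-up 6–18: λ = 0.05776; P = (0.7071 − 0.3536)/(0.05776 × 12) = 0.510; E[X] = 0.490 × 17.31 = 8.48.

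Median 4, follow-up 6–18: λ = 0.1733; P = (0.3536 − 0.0442)/(0.1733 × 12) = 0.149; E[X] = 0.851 × 5.77 = 4.91.

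The table uses cohorts of 30, the approximate Phase 1b cohort size. The plain median and third quartile are averages over simulated cohorts. The true third quartile is twice the median. All times are in months.

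| True median | Follow-up | Censored | Plain mean (true) | Plain median | Plain Q3 (true) |
|---|---|---|---|---|---|
| 4 | 12–24 | 5% | 5.5 (5.8) | 4.1 | 7.9 (8.0) |
| 4 | 6–18 | 15% | 4.9 (5.8) | 4.1 | 7.2 (8.0) |
| 6 | 12–24 | 14% | 7.5 (8.7) | 6.1 | 11.4 (12.0) |
| 6 | 6–18 | 27% | 6.3 (8.7) | 5.8 | 9.1 (12.0) |
| 8 | 6–18 | 37% | 7.3 (11.5) | 7.0 | 10.4 (16.0) |
| 12 | 12–24 | 36% | 11.1 (17.3) | 11.4 | 16.1 (24.0) |
| 12 | 6–18 | 51% | 8.5 (17.3) | 8.4 | 11.8 (24.0) |

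The two rows for a true median of 12 have identical survival, yet their mean OS is 11.1 and 8.5.

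**4. Against Kaplan-Meier.** For median 12 and follow-up 6–18, the Kaplan-Meier median is not reached in about 19% of cohorts; in those, the plain median averages about 8.9. The typical Kaplan-Meier median is about 12 if not-reached cohorts are ranked above all others, and about 11.2 among cohorts that reach it. For median 18 and follow-up 12–24 (50% censored), the plain median averages 13.8. The Kaplan-Meier median is not reached in 26% of cohorts, where the plain line would print about 14.7.

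**The case against.** The strongest reply is that little depends on the sentence. OS is secondary, all analyses are descriptive (Protocol 7), and no decision uses a plain mean or quartile. The Kaplan-Meier median and rates come first in the same item. The figure, "K-M plot of OS for safety population", is unaffected, and the survival listing shows "last known alive date, death date, time to death" for each subject, so a careful reader can see the censoring. This stands, and it limits the importance of the point.

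Second, the SAP does not say that censored times are treated as deaths. Median and quartiles are ordinary Kaplan-Meier outputs, so a Kaplan-Meier reading is possible. It fits poorly: the word *also* sets the summary apart from the Kaplan-Meier analysis, the median would be requested twice, and a plain SD, minimum and maximum are not Kaplan-Meier outputs. A deaths-only reading sits badly with the stated safety population and, under independent censoring, would be biased lower still.

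Third, the large discrepancies need longer survival and heavy censoring, which the documents neither state nor exclude. Protocol 5.2.4 follows patients until death, loss to follow-up, withdrawal of consent or study termination, so censoring may be light at the end. In the scenarios with true medians of 4 or 6 months, the plain median is nearly right and only the mean and upper quartile move. That also stands. It does not rescue the mean, which is low under any censoring.

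**Conclusion.** The point holds. On the natural reading, the added summary repeats extent of follow-up under an OS label. That its mean is too low as a mean survival time whenever anyone is censored needs no distributional assumption.

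The size does rest on assumptions: exponential survival, independent uniform censoring and 30 subjects per cohort. The mean is 5% to 27% low for true medians of 4 and 6 months, and about half the true value for a true median of 12 with 6 to 18 months of follow-up. The third quartile falls when censoring precedes it. The median is close to right when little censoring precedes it, and too low otherwise.

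The consequence is a misleading row in the OS table. The sentence should be corrected, but the planned Kaplan-Meier estimates are sound and need no change.

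**What to change.** Delete the descriptive sentence from SAP 7.5.2. Alternatively, replace it with the Kaplan-Meier 25th, 50th and 75th percentiles of OS with 95% CIs, printed as not reached where that applies. If a mean is wanted, specify a restricted mean survival time with a stated horizon. Keep the plain mean, SD, median and range under extent of follow-up only, adding the quartiles there if they are useful.

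The cost is SAP wording. The planned Kaplan-Meier analysis already yields the percentiles, and the follow-up item already covers the descriptive summary. No new data are needed.

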**3.4 Discontinuation of Patients following any Treatment with Study Drug**

Patients **must** discontinue study drugs for any of the following reasons:

- Withdrawal of informed consent (patient’s decision to withdraw for any reason)
- Any clinically significant AE, abnormal laboratory test results, or intercurrent illness which, in the opinion of the Investigator, indicates that continued participation in the study is not in the best interest of the patient
- Patients who are required to have prohibited concomitant medications

- Pregnancy
- Termination of the study by the Sponsor
- Loss of ability to freely provide consent through imprisonment or involuntary incarceration for treatment of a psychiatric or physical (e.g., infectious disease) illness
- Documented disease progression or clinical deterioration while receiving active study therapy
- Non-compliance by the patient

All patients who discontinue study treatment should comply with protocol specified follow-up procedures as outlined in Section 5.2.4. The only exception to this requirement is when a patient withdraws consent for all study procedures or loses the ability to consent freely (i.e., is imprisoned or involuntarily incarcerated for the treatment of a psychiatric or physical illness).

If a patient was discontinued, the reason for discontinuation must be entered on the appropriate CRF. The date and reason for cessation of cabiralizumab and/or nivolumab will be documented, and the Investigator must make every effort to perform the End-of-Treatment Visits. Adverse event reporting will continue until 100 ( $\pm 7$ ) days after the last dose of study drug or until initiation of subsequent anti-cancer therapy. Patients with ongoing SAEs will be followed until resolution or stabilization.

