#### **4.3.6 Infusion Delays and Missed Doses with Cabiralizumab and Nivolumab**

In case an infusion cannot be administered at a scheduled visit, it must be administered as soon as possible. If the delay is between 1 and 7 days, the procedures at the original scheduled visit should be performed. If the delay is more than 7 days, the infusion at the original scheduled visit will be considered a missed dose and the procedures at the next visit should be performed. If the delay is longer than 7 days, subsequent visits will follow a 2-week (or 3-week in Phase 1a 3-week dosing regimen cohort) dosing interval. If the delay is less than 7 days, the original dosing schedule should be followed. The time between two treatment cycles should be no less than 12 days.

Patients may miss up to up to 6 weeks between doses and may resume the study drug if the event returns to baseline or  $\leq$  Grade 1 within 6 weeks of treatment interruption. Omission of additional dosing longer than 6 weeks for AEs will necessitate the patient’s discontinuation from the study unless allowed by the Sponsor’s Medical Monitor or designee. Patients may miss doses in the

course of participation in the study, including missed doses for scheduled vacations or other personal reasons as needed, but not more than 6 weeks unless approved by the Sponsor's Medical Monitor or designee.

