### 6 STUDY PERIODS, TREATMENT REGIMENS

### 6.1 Study Periods

The study will consist of 3 periods including screening (up to 28 days), treatment, and follow-up. **Screening:** Subjects who have fully consented to participation in the study will undergo screening assessments within 28 days (4 weeks) prior to administration of the first infusion of study treatment.

**Treatment cycles**: (including end of the DLT period and Phase-1a extended treatment period.) For subjects in the monotherapy cohorts: cabiralizumab infusion administered as a 30-minute IV infusion on Day 1 of each 14-day treatment cycle.

For the combination therapy: nivolumab administered first as a 30-minute IV infusion, with a 30to 60-minute rest, followed by a 30-minute infusion of cabiralizumab on Day 1 of each 14-day treatment cycle.

For cohort 1aD (Subjects in 3-week dosing regimen cohort): Study drugs on Day 1 of each 21-day treatment cycle.

**End-of-Treatment Follow-up Period:** All subjects should return to the clinic 28 ( $\pm$ 7) days and 100 ( $\pm$ 7) days from their last dose of study drug to complete the End-of-Treatment Follow-up

Period, irrespective of whether a subject is discontinued from the study drug at a planned visit or mid-cycle. Subjects should continue onto Long-Term Follow-up after completing the End-of-Treatment. Subjects will be followed every 12 ( $\pm 2$ ) weeks for survival, or more frequently as needed.

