### 7.4.1 Study Therapy

Summary:

Descriptive statistics will be provided by treatment for the following:

- Exposure to cabiralizumab (weeks)
- Exposure to nivolumab (weeks)

Exposure (weeks) is defined as the (number of days between start date of first injection and stop date of last injection + 21)/ 7 for Cohort 1aD1, and (number of days between start date of first injection and stop date of last injection + 14)/ 7 for all the other cohorts.

- Total cabiralizumab dose administered (mg and mg/kg)
- Total nivolumab dose administered (mg and mg/kg)
- Number of cabiralizumab doses administered
- Number of nivolumab doses administered
- Relative Dose Intensity of cabiralizumab and nivolumab

Relative dose intensity is defined as ([total dose administered in mg/kg]/ [planned total b dose])\*100, where planned total dose is the prescribed starting dose in mg/kg times the exposure to study drug divided by 14 and 21 for all the cohorts except for 1aD1 and cohort 1aD1, respectively.

In addition, number and percentage will be provided for the subjects with relative dose intensity <50, 50-<70, 70-<90, 90-<110 and >=110.

Listing:

- Study drug administration details will be presented in a listing.
- Calculated exposure parameters for all the subjects

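### The PFS sensitivity analysis dates every clinical progression at last dose + 14 days, which misdates events after a held dose and overlooks the 21-day cycle of cohort 1aD1

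*SAP*

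**What the plan says.** SAP 7.5.2 lists PFS by investigator assessment, PFS by central review, and a pancreatic subgroup by prior lines of therapy. It then adds: "Sensitivity analysis will be performed for the above PFS analyses by treating clinical PD as event as well". The date follows from a single sentence: "Last dose date + 14 days is considered as event date for clinical PD". No cohort is excepted, held doses are not mentioned, and no reason is given for the offset.

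The main PFS analysis works differently. In SAP Table 3 the event is death or first RECIST progression, "whichever is earlier (excludes clinical progression"). A patient with neither is censored at the last evaluable assessment.

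Other parts of the documents that bear on the rule:

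- SAP 7.5 sets the PFS population: "The summaries for OS and PFS will be performed for safety population". That includes cohort 1aD1.
- SAP 6.1 gives the schedule for that cohort: "Study drugs on Day 1 of each 21-day treatment cycle". For exposure, SAP 7.4.1 adds a tail that respects it ("stop date of last injection + 21)/ 7 for Cohort 1aD1") and uses 14 days for every other cohort.
- Protocol 4.3.6: "Patients may miss up to up to 6 weeks between doses". Protocol 4.3.5 and 4.3.6 allow longer gaps with approval.
- During a hold, Protocol 4.3.2 asks for re-evaluation at least weekly, and Protocol 4.3.5 keeps tumour assessments on schedule.
- Protocol 3.4: "The date and reason for cessation of cabiralizumab and/or nivolumab will be documented".

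**The concern.** An offset of 14 days is natural when deterioration is found at the next two-weekly visit. It does not fit a patient whose next dose was held and who deteriorated during the hold. That patient is still being seen and scanned, yet the event is moved back to the day the held dose was due. If a scan in between showed no progression, the sensitivity analysis records an event before a date on which the patient was documented as progression-free. That scan date is also where the main analysis would censor the patient if no RECIST progression or death followed and no other censoring rule applied first.

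For some patients the rule supplies the whole event time. A patient with clinical progression, no post-baseline scan and no death is censored at first dose in the main analysis, so contributes PFS time only in the sensitivity analysis. A sensitivity analysis meant to test how clinical progression is handled should not add avoidable dating error.

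**Working it through.** There is no sample size, power or event count to reproduce. The plan's figure is the 14-day offset, so the check is date arithmetic, followed by an illustration at cohort level.

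**1. Consistency with the SAP's own tails.** SAP 7.4.1 uses 14 days for all cohorts except 1aD1, and 21 days for 1aD1. The offset in 7.5.2 matches the former and differs from the latter by 21 − 14 = 7 days (7 / 30.4375 = 0.23 months).

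**2. Error for one patient.** Let g be the days from last dose to actual clinical progression. Assigned date minus actual date = 14 − g.

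| g (days) | 14 − g | Months | Direction |
|---|---|---|---|
| 5 | +9 | 0.30 | late |
| 14 | 0 | 0 | correct |
| 21 | −7 | 0.23 | early |
| 28 | −14 | 0.46 | early |
| 42 (limit without approval) | −28 | 0.92 | early |
| 56 (needs approval) | −42 | 1.38 | early |

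**3. Event before a clean scan.** On two-weekly dosing, Cycle 4 Day 1 is Day 1 + 3 × 14 = Day 43. Suppose the dose due on Day 57 is held and clinical progression is found on Day 75 (g = 32).

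- The rule gives Day 43 + 14 = Day 57, which is 18 days early.
- With Day 57 as the nominal 8-week scan, the ±7-day window (Protocol 5.3.2.1.1) is Days 50 to 64.
- A scan on Day 60 could show no progression, three days after the assigned event.
- With no later RECIST progression, death or scan, Table 3 would censor this patient at Day 60.

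**4. Cohort 1aD1 without any hold.** Doses fall on Days 1, 22 and 43, and the next is due on Day 64. Clinical progression found at that visit is dated Day 43 + 14 = Day 57, 7 days early. The cohort is about 10 of 295 planned patients.

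**5. Size at cohort level.** The documents give neither the share of clinical progressions nor how often they follow a hold, so these inputs are assumptions: 30 patients; uncensored exponential PFS with median 2 or 4 months and no time below 15 days; 10 to 30% of events clinical; 25 to 50% of those after a hold; gap uniform on 15 to 42 days. Simulated mean shifts, early-dated events only (4,000 cohorts per setting):

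| Assumed median | Shift in median PFS (months) | Shift in 4-month rate (points) |
|---|---|---|
| 2 months | −0.011 to −0.063 | −0.11 to −0.58 |
| 4 months | −0.012 to −0.067 | −0.10 to −0.59 |

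A hand check gives the same order. The average gap is (15 + 42) / 2 = 28.5 days, so the average error is 28.5 − 14 = 14.5 days. Averaged over all patients, the shift is 0.10 × 0.25 × 14.5 = 0.36 days (0.012 months) at the low end and 0.30 × 0.50 × 14.5 = 2.2 days (0.07 months) at the high end.

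**The case against.** The best defence is that a fixed offset is a deliberate convention. Clinical deterioration is an investigator judgement with open-ended examples (Protocol 3.1.6.2) in an open-label study (Protocol 4.5). A mechanical date, set in advance, leaves no room for discretion. That argument has force, and it is a reason to keep an offset version alongside any other. It does not explain why the offset ignores the cycle length that the SAP uses elsewhere, or why an event may precede a scan without progression.

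The 1aD1 part is also thin. PFS is a Phase 1b secondary endpoint, and 1aD1 is a small Phase 1a cohort added for PK and safety. SAP 7.5 reduces groups too small for an analysis to counts and percentages. The inconsistency is real, but its consequence is slight.

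Some stronger readings are tempting, but the documents do not support them:

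- A reader might infer that the rule is early for everyone and so exaggerates the contrast with the main analysis. The error runs both ways: gaps under 14 days are dated late. The documents give no frequencies from which a net direction would follow.
- A reader might take the Protocol 3.4 date as the true event date, already on the case report form. That section concerns cessation of drug, not clinical progression. It places the reason on the form but says only that the date is documented. If that date is simply the last dose, using it would move events 14 days earlier than the present rule does.
- A reader might say that main PFS censors at clinical progression. Table 3 only declines to count it as an event. Later RECIST progression or death still counts unless another censoring rule applies first.

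**Conclusion.** The point holds as a minor one. Followed literally, SAP 7.5.2 misdates some clinical progressions: 28 days early at a 42-day gap, more after an approved longer hold, 7 days early in 1aD1 at the next planned visit, and late when progression is found within 14 days of the last dose. It can also place an event before a scan showing no progression. These statements need only the documents' own figures.

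The cohort effect rests on the assumed inputs above and is small: about 0.01 to 0.07 months in median PFS and 0.1 to 0.6 points in the 4-month rate. It would be tempting to divide 0.92 months by an assumed median of 2 to 4 months and report 23 to 46%. That sets one patient's largest shift without special approval against a cohort median that the documents do not give, and it describes no estimate the SAP will report.

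Only a sensitivity analysis of a secondary, descriptive endpoint is touched. Main PFS, ORR and OS are unaffected.

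**What to change.** Replace the dating sentence in SAP 7.5.2 with an ordered rule:

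1. Use the recorded date of clinical progression, if the database holds one.
2. Otherwise use the date of the decision to discontinue for clinical progression. Before naming this field, confirm that the cessation date in Protocol 3.4 is not simply the last-dose date.
3. If neither exists, use the last dose of either drug plus the cycle length: 14 days, or 21 for 1aD1. Saying either drug matters because Protocol 4.3.2 and 4.3.5 let one drug continue after the other stops, and the SAP does not define last dose in that case.
4. In all cases, do not date the event before the last evaluable scan showing no progression, by the assessor whose PFS is being analysed, or after death.

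The cost is SAP wording, a check of which date fields exist, and a few lines of programming. Steps 3 and 4 need no new data. The downside is that an investigator-recorded date is more discretionary than an offset in an open-label study. Keeping the last dose + cycle length version as a supplementary run answers that and shows whether the choice of date matters.
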